### **5.8.2. Analysis of Adverse Events of Special Interest**

Adverse events of special interest (AESI) include adjudicated arthropathies, AEs confirmed as SNS dysfunction and peripheral neurosensory events, and joint replacements meeting pre-specified AESI criteria. AESIs will be flagged in the database using predefined tick boxes to denote the events.

Summaries of AESI incidence by treatment group will include:

- Incidence of adjudicated arthropathy events
- Incidence of adjudicated arthropathies that meet destructive arthropathy criteria
- Incidence of joint replacements AESI events
- Incidence of sympathetic nervous system dysfunction AESI events
- Incidence of peripheral neurosensory AESI events

### **5.8.3. Clinical Laboratory Measurements**

Baseline clinical laboratory analytes and change from baseline in clinical laboratory analytes to each scheduled assessment time will be summarized with descriptive statistics for each treatment group.

Listings will be provided with flags indicating the out of laboratory range values.

A treatment-emergent Potential Clinically Significant abnormal value (PCSV) is a laboratory value that was normal or abnormal but not meeting PCSV criteria at Screening and Baseline but became abnormal and met PCSV criteria after treatment with study drug. Definitions of PCSV is listed in Section 10.3. Treatment-Emergent Potentially clinically significant values (PCSVs) will be summarized by treatment group.

For hs-CRP and alkaline phosphatase, plots of means and medians of the observed values and change from baseline over time will be presented by treatment group. Subgroup analysis will be performed for the following:

- Adjudicated Arthropathy category 1 (patients without / with AA)
- Adjudicated Arthropathy category 2 (patients without AA, patients with RPOA-1, and patients with other AA subtype except RPOA-1)
- Destructive Arthropathy category (patients without AA, patients with non-DA AA, patients with DA)

The above laboratory summaries will be constructed for the On-Treatment Period. Lab data collected during the Pre-Treatment and Post-Treatment Periods will be displayed in listings.

#### **5.8.4. Analysis of Vital Signs**

Vital signs (blood pressure, temperature and respiration rate) will be summarized by baseline and change from baseline to each scheduled assessment time with descriptive statistics.

A treatment-emergent Potential Clinically Significant abnormal value (PCSV) is a vital sign value that was normal or abnormal but not meeting PCSV criteria at Screening and Baseline but became abnormal and met PCSV criteria after treatment with study drug. Definitions of PCSV is listed in Section 10.3. Treatment-Emergent Potentially clinically significant values (PCSVs) will be summarized by treatment group.

The incidence of confirmed measurements suggesting orthostatic hypotension will also be summarized by treatment group.

The above vital sign summaries will be constructed for the On-Treatment Period. Vital sign data collected during the Pre-Treatment and Post-Treatment Periods will be displayed in listings.

#### **5.8.5. Analysis of 12-Lead ECG**

ECG parameters (Ventricular rate, Heart Rate, PR interval, QRS interval, QT interval and QTc interval) will be summarized by baseline and change from baseline to each scheduled assessment time by treatment group.

A treatment-emergent Potential Clinically Significant abnormal value (PCSV) is an ECG value that was normal or abnormal but not meeting PCSV criteria at Screening and Baseline but became abnormal and met PCSV criteria after treatment with study drug. Definitions of PCSV is listed in Section 10.3. Treatment-Emergent Potentially clinically significant values (PCSVs) will be summarized by treatment group.

ECG status (i.e. normal, abnormal) will be reported. Shift tables will be provided to present the post-baseline status according to the baseline status (normal or missing / abnormal) by treatment group.

#### **5.8.6. Physical and Neurological Examinations**

The percentage of patients with new-onset clinically significant abnormal physical examinations will be summarized by treatment group showing frequency and percentage by body system for each period as well as at the end of the period. Similarly summaries will be presented for neurological exam findings. These summaries will be constructed for the on-treatment period, post-treatment period and overall during the study.

#### **5.8.7. Analysis of Other Safety Variables**

Other safety data includes the survey of Autonomic Symptoms, cases of AA and joint replacements.

##### Adjudicated Arthropathy

Adjudicated arthropathy events based on imaging data overall and by subtype will be summarized by treatment group based on the SAF. Time to first AA event will be summarized by Kaplan-Meier method. Cox regression model will be used for descriptively comparing each treatment group to placebo by obtaining hazard ratio estimates along with 95% confidence intervals. Swimmer plots depicting the length of the observation window per patient and indicating timepoints at which the initial event occurred, worsened and/or changed subtype category may be presented by treatment group.

Time to first DA event will be summarized by Kaplan-Meier method. Cox regression model will be used for descriptively comparing each treatment group to placebo by obtaining hazard ratio estimates along with 95% confidence intervals.

All-cause joint replacements of any joint will be summarized by treatment group. The number of replacements in joints that were positively adjudicated will be summarized by treatment group. Joint replacements will also be summarized by KL score of the affected joint at screening.

In the time to event analyses, Time to first event will be calculated as : (Date of the first event – Date of the first dose of study drug +1). Patients without an event will be censored at the last visit for AA and DA in the analysis.

##### Survey of Autonomic Symptoms

The number of patients reporting the presence of each symptom/health problem assessed will be presented by treatment group at each scheduled visit. The number of symptoms reported and total symptom impact score will be presented by treatment group at each scheduled visit.

##### All-cause Joint Replacements

The number and percentage of patients with all-cause joint replacements will be presented by treatment group On-Treatment and Post-Treatment Periods based on the SAFs. The number of replacements in joints that were positively adjudicated will be summarized by treatment group. Joint replacements will also be summarized by KL score of the affected joint at screening.

Additionally, the number and percentage of patients who reported joint replacements at the End of Study Phone Call will be summarized.

The time to JR is calculated as:

$$= \text{Date of JR} - \text{Date of first dose of study drug} + 1$$

Plots of the Kaplan Meier curves by treatment group (as randomized) of time to JR will be presented based on the SAF, regardless of what period in the study the JR occurred. Patients without an event will be censored at the last contact.

### **Data from Urgent Safety Measure Patients**

Limited safety summaries will be presented based on the USM Analysis set including TEAEs and summaries of AAs, DAs and all joint replacements.

## **5.9. Analysis of Pharmacokinetic Data**

Summaries of fasinumab concentrations in serum will be presented by nominal time point. Individual patient concentration data will be plotted by actual time. Plots of mean and median serum concentrations of fasinumab will be presented by nominal time.

Correlation analyses of fasinumab concentrations in serum vs efficacy and safety endpoints may be performed, as appropriate.

## **5.10. Analysis of Immunogenicity Data**

### **5.10.1. Analysis of ADA Data**

The immunogenicity variables described in Section 4.7 will be summarized using descriptive statistics.

Immunogenicity will be characterized by ADA responses and titers observed in patients in the ADA analysis set. ADA response categories and titer categories are defined as follows:

ADA response categories:

- Pre-existing immunoreactivity, defined as either an ADA positive response in the ADA assay at baseline with all post first dose ADA results negative, OR a positive response at baseline with all post first dose ADA responses less than 9-fold over baseline titer levels.
- Treatment-emergent response, defined as a positive response in the ADA assay post first dose when baseline results are negative or missing.

The treatment-emergent responses will be further characterized as Persistent, Indeterminate or Transient.

- Persistent Response – Treatment-emergent ADA positive response with two or more consecutive ADA positive sampling time points, separated by at least 16-week period (based on nominal sampling time), with no ADA negative samples in between, regardless of any missing samples.

- Indeterminate Response –Treatment-emergent ADA positive response with only the last collected sample positive in the ADA assay, regardless of any missing samples.
- Transient Response –Treatment-emergent ADA positive response that is not considered persistent or indeterminate, regardless of any missing samples.
- Treatment-boosted response, defined as a positive response in the ADA assay post first dose that is greater than or equal to 9-fold over baseline titer levels, when baseline results are positive

Titer categories (Maximum titer values):

- Low (titer <1,000)
- Moderate ( $1,000 \leq \text{titer} \leq 10,000$ )
- High (titer >10,000)

The following analysis will be provided: Number (n) and percent (%) of ADA-negative patients (pre-existing immunoreactivity or negative in the fasinumab ADA assay at all time points) by treatment groups

- Number (n) and percent (%) of treatment-emergent ADA positive patients by treatment groups and ADA titer categories
  - Number (n) and percent (%) of persistent treatment-emergent ADA positive patients
  - Number (n) and percent (%) of indeterminate treatment-emergent ADA positive patients
  - Number (n) and percent (%) of transient treatment-emergent ADA positive patients
- Number (n) and percent (%) of treatment-boosted ADA positive subjects/patients by treatment groups and ADA titer categories

Listing of all ADA titer levels will be provided for patients with pre-existing, treatment-emergent and treatment-boosted ADA response.

### **5.10.2. Analysis of Neutralizing Antibody (NAb) Data**

The absolute occurrence (n) and percent of patients (%) with NAb status in the NAb analysis set will be provided by treatment groups.

### **5.10.3. Association of Immunogenicity with Exposure, Safety and Efficacy**

#### **5.10.3.1. Immunogenicity and Safety and Efficacy**

Potential association between immunogenicity variables and safety may be explored with a primary focus on the following safety events during the TEAE period: Injection site reaction (serious or severe and lasting 24 hours or longer)

- Hypersensitivity (SMQ: Hypersensitivity [Narrow])
- Anaphylaxis (SMQ: Anaphylactic reaction [Narrow])

Potential association between immunogenicity variables and efficacy and safety endpoints may be explored (e.g. scatter plot or spaghetti plot). The safety and efficacy analyses mentioned above will be conducted using the following categories: ADA positive patients, that is patients with treatment-emergent or treatment-boosted response.

- ADA negative patients, that is patients with pre-existing immunoreactivity or negative in the ADA assay at all time points.
- Patients with persistent treatment-emergent ADA response.
- NAb positive patients, that is ADA positive patients who were positive in the NAb assay at any time point analyzed.
- Maximum post-baseline titer in treatment-emergent or treatment-boosted ADA positive patients:
  - Low (titer <1,000)
  - Moderate ( $1,000 \leq \text{titer} \leq 10,000$ )
  - High (titer >10,000)

## 6. DATA CONVENTIONS

The following analysis conventions will be used in the statistical analysis.

### 6.1. Definition of Baseline for Efficacy/Safety Variables

Unless otherwise specified, the baseline value is defined as the last available valid measurement prior to randomization.

### 6.2. Data Handling Convention for Efficacy Variables

#### 6.2.1. Data Handling Convention for Efficacy Variables due to COVID-19 Pandemic

Due to public health measures implemented to address the world-wide COVID-19 pandemic, some sites may suspend onsite study visits or patients may opt not to attend. To mitigate data loss, patients may be contacted via telephone and the results of their efficacy measures transcribed verbally and entered into the eCOA devices. For analysis purposes, this data will be treated the same as efficacy data collected in an onsite visit and will be utilized in the efficacy analyses (Bellamy 2002). Sensitivity analysis may be performed excluding data collected via telephone.

### 6.3. Data Handling Convention for Repeat Measurements

#### Orthostatic Hypotension data

This applies specifically to the data handling of repeat measurements in the assessment of orthostatic hypotension. Per protocol, if the initial vital assessments for orthostatic hypotension is consistent with the definition of orthostatic hypotension, the supine, standing blood pressure or pulse should be repeated up to 2 more times. The guideline for the repeat assessments are shown below:

Initial Assessment	Repeat Assessment 1	Repeat Assessment 2	Does patient meet OH criteria	Value to be used in the analysis
Does not meet OH definition	N/A	N/A	No	Initial Assessment
Meets OH definition - repeat	Does not meet definition - repeat	Does not meet definition	No	N/A
Meets OH definition - repeat	Does not meet definition - repeat	Meets OH definition	Yes, AE of OH reported	Repeat Assessment 2
Meets OH definition - repeat	Meets OH definition	N/A	Yes, AE of OH reported	Repeat Assessment 1

Baseline for the assessment of orthostatic hypotension vital assessments uses the last available assessment prior to the start of study drug. Measurements post-baseline will not be averaged. Rather frequency counts for patients meeting OH criteria for orthostatic hypotension will reflect the scenario as shown on the table.

### **Patient reported outcomes data**

Should there duplicate entries for patient reported outcomes data (not including diary data), the average of the entries will be used for questionnaires with numerical values such as the WOMAC. The worst category will be used in the analysis for questionnaires with categorical responses such as the SAS and JPQ.

## **6.4. Data Handling Convention for Missing Data**

Rules for handling missing data for primary and secondary efficacy variables are described in Section 4.5.1 and Section 4.5.2.

### **Handling of Adverse Event and Injection Site Reaction Severity**

If the severity of a TEAE is missing, it will be classified as “severe” in the frequency tables by severity of TEAEs.

### **Handling of Adverse Event Relatedness**

If the assessment of relationship of a TEAE to the study drug or study conduct is missing, it will be classified as “related”.

### **Handling of Adverse Events or Concomitant Medications with missing or partial dates**

*Imputation of AE and Concomitant Missing and Partial start dates:*

Every effort will be made to collect the start dates of all AEs and concomitant medications. However, in the case the start date of an AE or concomitant medication is incomplete or missing, it will be assumed to have occurred on or after the first dose of study medication, except if an incomplete date (e.g., month and year) clearly indicates that the event started prior to treatment. If the partial date indicates the same month or year of the first dose of study medication date, then the start date of the first dose will be imputed, otherwise, the missing day or month by the first day or the first month will be imputed.

*Imputation of Partial AE and concomitant Medication Partial end dates:*

When only year is present, missing AE/concomitant medication end day and month will be imputed to the earlier of (study end date, 31DECYYYY).

When both month and year present, missing AE/concomitant medication end day will imputed to the last day of the month.

There will be no attempt to impute completely missing AE or concomitant medication end dates. Events with an end date missing will be assumed to be ongoing at the time of data cut off.

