#### 5.1.1. Screening and Pre-Randomization

Prior to randomization, patients will undergo screening procedures, including X-ray of the shoulders, hips, and knees. Magnetic resonance imaging of the index and contralateral joint must be performed at screening and the results assessed by the central imaging vendor. In addition, an MRI will be performed on any knee or hip joint with a K-L score of  $\geq 3$ . Randomization visits cannot occur until there is confirmation from the central imaging vendor that there are no exclusionary findings on the X-rays and any required MRIs. During the screening period, all patients will continue to take their current treatment regimen for OA pain, which must include use of an oral NSAID on a regular basis, defined as approximately 4 days per week over the last 4 weeks.

Patients eligible for the study will complete a pre-randomization period, during which all pain medication, except for the study-provided rescue medication (acetaminophen/paracetamol), will be discontinued. The pre-randomization visit will be 7 to 10 days (7 days with a +3 day window) before randomization. Patients will discontinue and/or undergo a washout of, their standard-of-care pain medications for OA during the pre-randomization period. As needed, patients may take acetaminophen/paracetamol for pain relief according to the regional standard-of-care (see Section 7.2 for details). Acetaminophen/paracetamol must not be taken within 24 hours prior to the randomization visit.

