### **10.5. Additional Statistical Data Handling Conventions**

The following analysis and data conventions will be followed:

General rules for handling missing data:

- Rules for handling missing data for efficacy assessments due to missing individual item data will follow each questionnaire's instrument manual
- If the start date of an AE or concomitant medication is incomplete or missing, it will be assumed to have occurred on or after the intake of study drug, except if an incomplete date (eg, month and year) clearly indicates that the event started prior to treatment. If the partial date indicates the same month or year of the intake of study drug date, then the start date by the study drug intake date will be imputed; otherwise, the missing day or month by the first day or the first month will be imputed.
- No imputations for missing laboratory data, ECG data, vital sign data, or physical examination data will be made.

Visit windows:

- Assessments taken outside of protocol allowable windows will be displayed according to the CRF assessment recorded by the investigator.

Unscheduled assessments:

- Extra assessments (laboratory data or vital signs associated with non-protocol-specified clinical visits or obtained in the course of investigating or managing AEs) will be included in listings, but not summaries. If more than 1 laboratory value is available for a given visit, the first observation will be used in summaries and all observations will be presented in listings.

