#### **4.4. Prohibited Medications**

Opioid analgesic medications (including tramadol) are prohibited through the week 24 study visit. NSAIDs (oral or topical, except up to 150 mg/day of aspirin/5-ASA, which is permitted for cardiac prophylaxis) are prohibited until at least 16 weeks after the last SC study drug injection.

Other prohibited medications during the treatment period include:

- Any other investigational agent
- Medical or regular recreational use of marijuana
- Chondroitin sulfate
- Glucosamine
- Hyaluronic acid intra-articular injections
- Anticoagulants and antiplatelets (e.g., warfarin, heparins, factor Xa inhibitors, thrombin inhibitors, aspirin/5-ASA >150 mg daily, clopidogrel)
- Muscle relaxants including cyclobenzaprine, carisoprodol, orphenadrine, tizanidine (see protocol Section 7.7.2 for permitted muscle relaxants)
- Corticosteroids (topical, intranasal, and inhaled formulations are permitted), adrenocorticotrophic hormone
- Cyclosporine, methotrexate, mycophenolate mofetil, tacrolimus
- Azathioprine, sulfasalazine, hydroxychloroquine
- Interleukin-6 or interleukin-6 receptor antagonists
- Abatacept, ustekinumab
- Tumor necrosis factor antagonists
- IL-1 inhibitors, including diacerein
- Apremilast, and tofacitinib
- Combination therapy of diuretics with either an ACE inhibitor or ARB

The following variables will be summarized for prohibited medications:

- Number and percentage of patients using at least one prohibited medication during the treatment period
- Number and percentage of patients using at least one prohibited medication during the follow-up period.

- Number and percentage of patients with at least one prohibited NSAID use during the treatment period.
- Number of days patients used prohibited medications during the treatment period.
- Number of days patients used prohibited NSAID during the treatment period.

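### SAP 6.4 imputes partial start dates without consulting a recorded stop, and sets partial stop dates to month-end without a bound, so some pre-dose events and washed-out NSAIDs are filed as on-treatment

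*SAP*

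**What the plan says.** SAP 6.4 gives one set of date rules for adverse events and concomitant medications.

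- **Start dates.** A missing or incomplete start is presumed to fall on or after first dose, "except if an incomplete date (e.g., month and year) clearly indicates that the event started prior to treatment". The operative sentence is "If the partial date indicates the same month or year of the first dose of study medication date, then the start date" of first dose is imputed. Any other partial start goes to the first day or first month.
- **Stop dates.** With month and year known, the "missing AE/concomitant medication end day will imputed to the last day of the month". With only the year known, the stop is "imputed to the earlier of (study end date, 31DECYYYY"). With nothing known, "Events with an end date missing will be assumed to be ongoing at the time of data cut off".

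Protocol 10.5 has the same start rule ("If the partial date indicates the same month or year of the intake of study drug date") and no stop rule.

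Three other places use these dates. SAP 4.3 defines prior medication by a start before first dose, concomitant medication by a stop during or after the On-Treatment Period, and post-treatment medication by a start after that period. SAP 4.4 lists "Number and percentage of patients with at least one prohibited NSAID use during the treatment period" and the matching number of days. SAP 5.4 adds total prohibited-NSAID days, counted up to the arthropathy in patients who have one. Protocol 5.1.1 has every patient continue a pain regimen through screening "which must include use of an oral NSAID on a regular basis", then stop it 7 to 10 days before randomization.

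**The concern.** Two gaps stand side by side. First, the start rule looks only at the incomplete date. Nothing compares the imputed start with a stop date that is already recorded, so the rule can return a start later than the stop. Second, the stop rule has no upper bound at first dose or washout, although all patients stop an NSAID shortly before Day 1.

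The first gap affects the treatment-emergent tables. Adverse events are collected from consent, through up to 30 days of screening and the 7 to 10 day washout. SAP 5.8.1 keeps pre-treatment events in a separate listing, so a misfiled event moves from that listing into the main tables. The second gap affects the prohibited-NSAID counts and days, which the SAP plans to set beside adjudicated arthropathy.

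**Working it through.** The documents state no figure for this point, so there is none to reproduce. The rules are applied literally below.

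**Adverse event, worked example.** Start recorded as March 2019, stop 8 March, first dose 20 March. The start month equals the first-dose month, so the imputed start is 20 March. That is 20 − 8 = 12 days after the event ended, and by onset it is treatment-emergent. The exception does not apply, because March alone does not show a start before 20 March.

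**How often a pre-dose onset shares the first-dose month.** In a 30-day month with Day 1 spread evenly, an onset k days earlier shares the month with probability (30 − k)/30:

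- k = 5: 25/30 = 83%
- k = 10: 20/30 = 67%
- k = 20: 10/30 = 33%

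If onsets are uniform over the 37 to 40 days before dosing (an assumption), and every first-dose day in 2018 and 2019 is counted, 37% to 40% of month-and-year starts are reset to first dose. For year-only starts the figure is 94% to 95%. The impossible ordering arises in those that also have a recorded stop before first dose.

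**Medication with a known pre-dose stop.** If the start is wholly missing, or partial within the first-dose month or year, it is placed on or after first dose. Under SAP 4.3 the drug is then not prior (its start is not before first dose) and not concomitant (its stop is before the On-Treatment Period). When the start is set to first dose, it is not post-treatment either. It leaves all three tables.

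**Washout NSAID, day of stop missing.** With a true stop k days before Day 1, a 30-day month and Day 1 on day d, the stop shares the month when d runs from k + 1 to 30. The imputed stop is day 30, so the false on-treatment days are 30 − d + 1.

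- Share carried to or past Day 1 = (30 − k)/30
- Mean false days among these = (31 − k)/2

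| k | Share, 30-day month | Mean days, 30-day month | Share, 2018–2019 calendar | Mean days, 2018–2019 calendar |
|---|---|---|---|---|
| 7 | 23/30 = 77% | 24/2 = 12.0 | 77% | 12.2 |
| 10 | 20/30 = 67% | 21/2 = 10.5 | 67% | 10.7 |

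The maximum is 30 − 7 = 23 days in a 30-day month. With only the year recorded and a study end after 31 December, 97% to 98% of stops move to or past Day 1. The mean is then about 129 false days, capping each record at 168.

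**Whether one check cures both.** A rule that the start may not follow a recorded stop catches the adverse-event example. It does nothing for the NSAID. With stop month March and first dose 20 March, the stop becomes 31 March, giving 31 − 20 + 1 = 12 false days, while start and stop remain in valid order. The NSAID case needs its own bound.

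**The case against.** The strongest reply is that the start rule is a prespecified, conservative convention. It matches Protocol 10.5, and the neighbouring SAP rules also lean toward over-counting harm: missing severity becomes severe and missing relatedness becomes related. That defends the default when no stop is known. It does not defend a start placed after a recorded stop.

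A second reply is that the trigger may be uncommon. Washout is tied to a dated visit, medications are reviewed at screening, pre-randomization and baseline, and the SAP commits to pursuing start dates. This stands. The percentages above apply only to records with partial dates, and a year-only stop for a drug stopped at a clinic visit should be rare.

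A reader might also infer more than the documents support:

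- **That the missing start-versus-stop comparison causes the NSAID error.** It does not; the unbounded stop rule does. An NSAID with a known pre-dose stop is never concomitant under SAP 4.3.
- **That long-standing drugs in general vanish from the prior-medication table.** The exception protects any partial start in an earlier month or year. Only wholly missing starts, or starts ambiguous within the first-dose month or year, are exposed.
- **That the rule manufactures the NSAID exposure linked to destructive arthropathy.** The Protocol Introduction ties that risk, for another antibody of the class, to chronic use beyond 90 days. A month-end stop adds at most about 23 days. Only year-only stops could exceed 90.
- **That efficacy is affected.** The primary estimand in SAP 5.7.1 applies whether or not prohibited medication was taken. Per-protocol exclusion for NSAID use runs through deviation code 8.06 in SAP 10.4, and the SAP does not say that imputed dates feed it.

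**Conclusion.** The point holds in two separate parts. The start rule, as written, gives an impossible result whenever a partial start in the first-dose month or year meets a recorded stop before first dose. Such an event is counted as treatment-emergent, and such a medication is lost from the prior-medication table. The stop rule carries about 67% to 77% of day-missing washout NSAID stops to or past Day 1, adding about 11 to 12 days each on average to descriptive summaries.

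These sizes assume Day 1 is spread evenly over the month and the NSAID was in fact stopped 7 to 10 days before it. The total effect cannot be stated, because the number of partial dates is not given. The errors come from pre-dose records in a randomized, double-blind trial, so they should be about equal across arms. They would inflate counts and pull relative comparisons toward no difference, not favour one arm. This is worth correcting because the rule is wrong on its face and cheap to repair. It does not threaten the primary result.

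**What to change.** Amend SAP 6.4 before database lock.

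1. An imputed start may not be later than a recorded stop. Any adverse event or medication whose recorded stop precedes first dose is classed as pre-treatment or prior. Keep the present default of on or after first dose when no stop is known.
2. For an NSAID recorded before first dose (at screening or in medication history) with a partial stop in the first-dose month or year, bound the imputed stop at the day before first dose only if the record shows it was stopped for washout and no later NSAID use is recorded. Otherwise keep the current rule, and report these records separately or in a sensitivity summary.

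Do not add a general presumption that every ambiguous medication start is before first dose. It would backdate drugs truly started after Day 1. An unconditional cap on washout NSAIDs would likewise erase real continued use.

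The cost is a few lines of text and some programming. The documents do not describe an indicator that a drug was stopped for washout, so its availability must be confirmed. There is a small risk of under-counting continued NSAID use where the washout record is wrong.
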